9.0 References

## EMPOWER-II

### 1.0. Background & Significance

Young women treated for childhood cancer with chest radiotherapy (RT) have a very high risk of breast cancer. By age 50, almost one in three women treated with chest radiotherapy (RT) for a childhood cancer will be diagnosed with breast cancer. Risk is highest among Hodgkin lymphoma survivors, with a cumulative incidence of 35% by age 50. For perspective, the cumulative incidence of breast cancer, by age 50, among BRCA1 carriers is 31%; among women in the general U.S. population, it is < 5%.

Survival and long-term outcomes following breast cancer among childhood cancer survivors is highly dependent upon stage of disease at diagnosis. In two systematic reviews, we reported that the clinical characteristics of tumors (e.g., hormone status, location) in women treated with chest RT were similar to those among women with sporadic breast cancer. When detected at a node negative early stage, breast cancer in this high-risk population is highly curable. There are two very important therapeutic limitations in treating women for breast cancer following chest RT for a childhood cancer. First, using breast irradiation for local control of disease is rarely used due to the risk of radiation-induced tissue and fat necrosis in these women who have already been treated with high dose radiation to the breast. Second, for women with node-positive breast cancer, therapy for the childhood cancer limits the options for adjuvant therapy for secondary breast cancer. Doxorubicin, an anthracycline, remains a mainstay in the treatment of advanced node-positive breast cancer. However, if anthracyclines were used to cure the childhood cancer, they are relatively contraindicated in the treatment of breast cancer due to the substantially elevated risk of congestive heart failure. Of note, anthracyclines are commonly used in the treatment of childhood cancer. Reflecting the late stage at which most breast cancer is diagnosed in this population and the limitations in therapeutic options, the 10-year breast cancer-specific mortality is 19%; the 10-year all-cause mortality after a diagnosis of breast cancer is 32%.

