## 3.0 Participant Recruitment and Enrollment

We will enroll 320 women from the Childhood Cancer Survivor Study (CCSS), alternatively known as the Long-Term Follow-Up Study (LTFU) to participants. The CCSS is a multi-institutional, multi-disciplinary collaborative research resource established to systematically evaluate long-term outcomes among children

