## EMPOWER-II

diagnosed with cancer who survived five or more years from diagnosis. Participants will be recruited in three waves (97/wave) by the CCSS Coordinating Center, which has extensive experience recruiting for our studies. We anticipate enrolling 97 participants in Year 1 and then the remaining 194 in Year 2. All eligible members of the CCSS cohort will be identified by the CCSS Statistical Center. We will randomly sample CCSS members from this eligibility list to contact regarding participation in this study.

An introductory letter of invitation will be sent via e-mail by the CCSS Coordinating Center. Included in this e-mail will be (1) an invitation to join the EMPOWER-II study; (2) instructions on how to download the Eureka platform and (3) a brief summary of study activities. A second letter will be sent to non-responders via regular mail. After 3 weeks, a telephone interviewer from the CCSS Coordinating Center will then call potentially eligible cohort members who fail to respond to 2 invitation letters and invite them to participate. After 3 weeks, a final invitation letter will be sent via regular mail. Once interested participants have downloaded the Eureka app, they will receive push notifications leading them to an FAQ sheet and eligibility checklist within the app. Eligible participants will then receive an electronic consent form via the app along with a HIPAA waiver, and a link to the privacy policy of Eureka. We will continue attempting to accrue subjects from the eligibility list until 320 members have been randomized in the study. With over 1,400 women in the CCSS potentially eligible for this study and the high participation rate in EMPOWER-I, we do not anticipate a problem in enrolling 320 participants. During the study enrollment, there will be an estimated 1,456 women who fulfill the eligibility criteria.

All participating survivors will be compensated \$50 for each survey completed at baseline and at the end of the study (\$100 total for each survivor). We will also compensate PCPs for their time in answering the short survey at baseline and at the end of the study. We will compensate at the same rate as the survivor participants: \$50 per survey (\$100 total for each PCP).

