### 3.2 Randomization and Stratification

After completion of the baseline questionnaire, participants will be randomly assigned, in a ratio of 1:1:1, to one of the three groups (control, PA, PA+PCP). Randomization will be stratified by age at study enrollment (25-39,  $\geq 40$ ), by cancer diagnosis (Hodgkin lymphoma, other cancers), and by receipt of a previous breast imaging exam (either mammogram or breast MRI) in the previous 24 months (yes, no). Because we did not observe a difference in mammography or breast MRI surveillance between white, non-Hispanic and minority survivors in EMPOWER-I, we will not stratify by race/ethnicity. However, we will oversample from minorities in CCSS with the goal of having 18% of participants in the trial coming from minority populations. Further, since only a small percent of participants had a family history of breast cancer (<1%) or did not have a PCP (8%), we will not stratify by these two factors. However, we will have tailored push notifications / video vignettes for women without a PCP that are intended to help them find one. These three stratification factors were chosen because of the desire to maintain balance between the three arms with respect to age, cancer diagnosis, and recent single imaging study while simultaneously keeping the number of strata to a minimum and ensuring stratum size does not get too small. We will use a permuted block randomization scheme with a block size of three and six. A computer-based random number generator will be used to generate the sequence of assignments in advance.

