Our assessment of the downstream costs of the intervention, as well as the cost of the intervention itself, will allow us to perform a limited cost-effectiveness analysis. Specifically, we will estimate the cost per additional patient screened and the cost per additional breast cancer case detected as a result of the intervention. Because these health outcomes do not capture events that follow breast cancer diagnosis, our cost estimates will not include the costs of events that follow diagnosis (e.g., costs of breast cancer treatment). As previously mentioned, we will not conduct formal hypothesis tests on the economic outcomes given the primary focus of the trial on non-economic endpoints (and sample size requirements associated with these endpoints). Resource utilization and cost data are typically skewed, and therefore the sample size of the trial will likely be insufficient to detect significant differences in costs between study arms. The economic impact of the intervention will be evaluated using standard incremental cost-effectiveness analysis methods, and sensitivity analysis will be used to assess the impact of assumptions and uncertainty on results and conclusions. This analytic approach is appropriate in economic studies that "piggyback" randomized trials.

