### 6.2 Sample Size and Power

The primary aim involves two pair-wise comparisons of equal importance. For each comparison, we fix the probability of a Type I error at 0.025 in order to maintain the overall probability of a Type I error at 0.05. We powered the study to detect a difference of 20% for each pair-wise comparison assuming equal randomization to each of the three arms and that the proportion of women in the control group who will have a mammogram and an MRI will be approximately 10% based on our previous work. Table 1 shows the power we expect to have using two-sided Mantel-Haenszel tests and indicates that we should have sufficient power to detect a clinically meaningful difference even if the proportion of women in the control arm with the primary endpoint is somewhat higher than we expect. The power calculation of the Cochran-Mantel-Haenszel tests assumes a common risk ratio among the strata, that all strata generate the same proportion for the control arm and intervention arm.

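### The planned cost per additional breast cancer detected divides by an expected difference of fewer than one case per two-arm comparison

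*Combined protocol and SAP*

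**What the plan says.** The cost-effectiveness paragraph in section 6.0 (Statistical Analyses) names two ratios. One is the cost per additional patient screened. The other is "the cost per additional breast cancer case detected as a result of the intervention". The same paragraph calls the analysis limited, rules out formal tests on economic outcomes, concedes that the sample is probably too small for cost differences because such data are skewed, and refers in general terms to standard incremental methods and sensitivity analysis. The preceding paragraph specifies one sensitivity analysis, over a range of unit costs.

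The inputs to the denominator are elsewhere in the document:

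- Section 3.0 sets the total: "We will enroll 320 women from the Childhood Cancer Survivor Study (CCSS"). It also says "Participants will be recruited in three waves (97/wave"), which makes 291.
- Section 3.2: "participants will be randomly assigned, in a ratio of 1:1:1, to one of the three groups".
- Section 6.2: "We powered the study to detect a difference of 20% for each pair-wise comparison", with about 10% of controls expected to have both tests.
- Section 1.0, on risk: "By age 50, almost one in three women treated with chest radiotherapy (RT) for a childhood cancer will be diagnosed with breast cancer".
- Section 4.0 gives an 18-month trial.

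The document states no expected number of cancers, no yield per woman screened, and no rule for reporting the ratio when the arms differ by zero cases or in the wrong direction.

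**The concern.** An incremental ratio needs a denominator that is clearly different from zero. Here it is a between-arm difference in cancers among roughly a hundred women per arm over 18 months. If the expected difference is a fraction of a case, the computed ratio depends mainly on chance: undefined at zero, reversed in sign below zero, and at one case liable to be halved by one more diagnosis or made undefined by one fewer. Varying unit costs changes only the numerator. At stake is a cost-per-cancer figure that a reader could take as a trial result when one or two diagnoses determine it. No primary or secondary test of screening is affected.

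**Working it through.** **The plan's own figure.** The document gives no expected case count, so the nearest stated figure is the power for the screening contrast behind the denominator: 90% for 10% against 30% (Table 1). Section 6.2 says "we fix the probability of a Type I error at 0.025" for each comparison, "using two-sided Mantel-Haenszel tests". With z = 2.241 and 97 per arm, the normal approximation is Φ[(0.20 − 2.241 × √(2 × 0.20 × 0.80/97)) / √((0.09 + 0.21)/97)] = Φ(0.0713/0.0556) = Φ(1.28) = 90.0%. With 107 per arm it is 92.8%, or 90.1% with a continuity correction. The contrast and arm size are therefore understood as the plan intends.

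**Step 1: additional women screened.** 320/3 ≈ 107 per arm, and 107 × (0.30 − 0.10) = 21.4. With 291/3 = 97 per arm it is 19.4.

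**Step 2: yield y (cancers detected per woman screened).** This is an assumption. Spreading section 1.0's risk evenly over ages 25 to 50 gives, for 18 months:

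- simple division: 0.33/25 × 1.5 = 2.0%;
- constant hazard with 30% by age 50: −ln(0.70)/25 × 1.5 = 2.1%;
- constant hazard with 33%: −ln(0.67)/25 × 1.5 = 2.4%.

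The working range is 1% to 4%. An extreme of 6.3% comes from packing the 35% quoted for Hodgkin lymphoma into ten years: 1 − exp(ln(0.65)/10 × 1.5).

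**Step 3: expected additional cases.** E = n × (0.30 − 0.10) × (y − c), where c is the probability of detection in a woman without both tests. At n = 107, y = 2% and c = 0, E = 21.4 × 0.02 = 0.43. E reaches one case only when y ≥ 1/21.4 = 4.7% (1/19.4 = 5.2% at 97 per arm), with nothing found outside combined screening.

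**Step 4: chance that the difference is zero or negative.** Cases are independent binomials. At y = 2% and c = 0 the per-woman probabilities are 0.30 × 0.02 = 0.006 and 0.10 × 0.02 = 0.002.

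- Both arms zero: 0.994^107 × 0.998^107 = 0.525 × 0.807 = 0.424.
- Both arms one: 0.339 × 0.173 = 0.059. Both arms two: 0.002.
- Exactly equal: 0.485. Active arm below control: 0.108. Zero or negative: 0.593.

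| Yield y | E, c = 0 | P(≤ 0), c = 0 | E, c = y/2 | P(≤ 0), c = y/2 |
|---|---|---|---|---|
| 1% | 0.21 | 75% | 0.11 | 67% |
| 2% | 0.43 | 59% | 0.21 | 58% |
| 3% | 0.64 | 49% | 0.32 | 54% |
| 4% | 0.86 | 42% | 0.43 | 52% |
| 6.3% | 1.34 | 31% | 0.67 | 48% |

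(107 per arm, 10% against 30% screened. At 97 per arm with c = 0 and y = 2%, E = 0.39 and P = 62%.)

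**Step 5: if the difference is positive.** At y = 2% and c = 0, about 72% of positive differences are exactly one case and about 94% are one or two.

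**The case against.** **The yield is not in the documents.** This stands. Eighteen-month incidence is only a stand-in for screening yield. Women who had both tests in the previous 24 months are excluded, so many participants may be overdue for at least one test, and a first screen can find cancers that arose earlier. There is no upper age limit. Both could raise the yield; a recent single test, which eligibility allows, could lower it. A reader might infer that the ratio will most likely be undefined or negative. The documents do not support that: with no detection outside screening the probability drops below one half from a yield of about 2.9%. Over yields of 1% to 6.3% and both arm sizes it runs from about 31% to 77%. Nor do they support a firm statement that the expected difference is under half a case: the 2.4% hazard reading gives 21.4 × 0.024 = 0.51 cases and 55%.

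**The comparison is not fixed.** This also stands. Section 6.0 refers to the intervention without naming arms. Pooling the active arms (about 213 against 107) at a 2% yield lowers the probability to 35%. The expected excess among the active women is still only 213 × 0.004 = 0.85 cases.

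**Women with one test can also be diagnosed.** True, and the effect is uncertain. If women without both tests are detected at half the rate, the expected difference halves, and at 2% the negative share rises from 11% to 32%.

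**A negative difference can still be reported.** Correct. Higher cost with fewer cases is dominance, so only an exact zero is strictly undefined.

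**The plan already has safeguards.** Only in part. The general sensitivity analysis is not confined to unit costs, but it names no method for this denominator. The small-sample concession concerns skewed costs, not case counts.

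**Conclusion.** The concern holds in limited form. At assumed yields of 1% to 4%, with about 107 women per arm and the planned screening contrast, the trial can expect about 0.2 to 0.9 additional cancers per two-arm comparison. The chance of a zero or negative difference is then roughly even: about 40% to 75%, and 59% at a 2% yield with no cancers found outside combined screening. At that yield a positive difference usually rests on one or two cases. The result depends on the assumed yield, on a two-arm comparison and on the planned effect being achieved. An expectation of one case or more needs a yield of at least 4.7% with nothing detected outside screening.

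The weight is low. The ratio is not among the objectives in section 2.1 (2.1.4 covers replication and resulting costs only), no test depends on it, and the companion ratio, with about 21 additional women in its denominator, does not share the problem.

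**What to change.** In the cost-effectiveness paragraph of section 6.0:

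- make cost per additional woman screened, with a bootstrap interval, the only ratio computed from trial counts, and name the arm comparison;
- report incremental cost and cancers detected by arm side by side, with exact intervals for the cancers;
- present any cost per cancer detected only as a labelled model estimate: additional women screened in the trial times an external yield, over a stated range of yields.

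This changes analysis-plan wording only; data collection is unaffected. The downside is that one exploratory ratio is no longer reported from trial counts.

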### Supplemental Imaging

We will tabulate the BI-RADS breast density assessment and look at the distribution of the categorical assessment by clinical review by age at the time of the mammogram (<40, 40+ years), menopausal status at the time of the mammogram (pre-menopausal, post-menopausal), age at childhood cancer diagnosis (<10, 10-20), and time from childhood cancer diagnosis (<15, 15-24, 25+ years).

The clinical review categories will be dichotomized to BI-RADS 1 and 2 (fatty replaced, scattered areas of fibroglandular tissue) vs BI-RADS 3 and 4 (heterogeneously dense, extremely dense). Our primary outcome

### 6.1 Missing Data

Every effort will be made to minimize missing data and participant drop-out, both among the women and their PCPs. The primary analysis is an intent-to-treat analysis and will include all women who are randomized to the study regardless of whether they complete the end-of-study assessment (participants who drop out will be counted as failures in this analysis). Secondary analyses will include exploratory comparisons restricted to women who complete the end-of-study assessment. If potential moderating and mediating factors are missing, we will use multiple imputation. We will explore missing patterns among the PCPs and may consider using multiple imputation if it is warranted.

### 6.2 Sample Size and Power

The primary aim involves two pair-wise comparisons of equal importance. For each comparison, we fix the probability of a Type I error at 0.025 in order to maintain the overall probability of a Type I error at 0.05. We powered the study to detect a difference of 20% for each pair-wise comparison assuming equal randomization to each of the three arms and that the proportion of women in the control group who will have a mammogram and an MRI will be approximately 10% based on our previous work. Table 1 shows the power we expect to have using two-sided Mantel-Haenszel tests and indicates that we should have sufficient power to detect a clinically meaningful difference even if the proportion of women in the control arm with the primary endpoint is somewhat higher than we expect. The power calculation of the Cochran-Mantel-Haenszel tests assumes a common risk ratio among the strata, that all strata generate the same proportion for the control arm and intervention arm.

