## 2.2 Hypotheses

We will test the following hypotheses:

For primary objective: Compared to C, women randomized to PA and PA+PCP will have significantly higher rates of breast cancer surveillance (breast MRI and mammogram) than women in the C group.

Given the primary focus of the trial on non-economic endpoints (and sample size requirements associated with these endpoints), we will not conduct formal hypothesis tests on the economic outcomes.

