## EMPOWER-II

A final attempt to collect study outcomes (mammogram, breast MRI, breast ultrasound, medical records and pathology) from 63 participants who are more than 3 months past the approximated 18-month study window will be done via 2 regular mailings, an email notification (sent by the Duke team), and a follow-up phone call from the CCSS Coordinating Center who will administer the questionnaires over the phone. The mailed packet will include 2 options to complete the end-of-study survey: a) a full survey set or b) an abbreviated version of the survey focusing on the main study outcomes (i.e. were they able to get their breast cancer screening tests done and where). PCP factors will also be collected for this group. This attempt extends this group's participation by up to a year. These participants have already completed the baseline survey but have not responded to multiple automated and email reminders within the initial 18-month study period. This extended timeline will not be applicable to those who are currently active in the study.

To collect information on PCP factors, the Duke team will administer the baseline and end-of-study surveys (print via fax) for the PCPs of the CCSS participants. We will ask women in the baseline survey for the name and contact information for their PCP and will solicit this information via the Eureka app for those who don't have one at baseline.

After completion of the baseline measurement questionnaire, participants will be randomly assigned, in a ratio of 1:1:1, to one of the three groups: control, patient activation (PA), or patient activation + primary care provider activation (PA+PCP). An overview of the 3 groups is presented in **Appendix I**. All participants will receive the mailed education materials used in EMPOWER-I.

Recurring notifications, sent through the Eureka App, will be added to remind participants of pending study activities. Also, a cost sharing survey and a Eureka App user experience survey will be added to the End of Study Questionnaire.

This study will use a 3-group comparative effectiveness design comparing:

- Targeted mailed educational materials (C) including a Survivorship Care Plan;

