## 6.0 Statistical Analyses

The primary analysis involves comparing the proportion of women with a self-reported breast MRI and mammogram in each intervention arm to C. In EMPOWER-I, we used self-report of the imaging studies. We also sought to obtain medical record (fax) confirmation of the self-reported imaging studies. We were successful in obtaining the proper reports for 85.7% of the participants. However, for the remaining 14.3%, we were unable to confirm the study due to lack of information provided by the participant regarding the imaging facility, the imaging facility being unable to locate records and the facility sending only partial information, despite multiple attempts to collect the data. Importantly, the findings were not substantively different when we repeated the analysis including only women with a fax-confirmed imaging study. Stratifying on the randomization strata, differences in these proportions will be estimated with stratum-adjusted proportions calculated using the weighted average of the stratum-specific differences and accounting for the sampling scheme. The Cochran-Mantel-Haenszel test will be used to test for differences between (1) PA and C, and (2) PA+PCP and C in an intent-to-treat analysis where women who do not complete the end-of-study assessment will be counted as not having had a breast MRI and mammogram. We will also perform a secondary analysis of women with a fax-confirmed imaging study. Based on EMPOWER 1 results, we do not expect results to differ based on race/ethnicity, but will verify this result here. The analytic methods for the secondary objectives will be the same as for the primary objective, using the Cochran-Manetel-Haenszel test to examine differences between the interventions (PA, PA+PCP) on breast cancer surveillance rates (breast MRI + mammogram) and on rates of each individual surveillance test.

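### The fixed 0.025 split of the two primary comparisons is valid, but Holm's step-down rule holds the same overall 0.05 and gives a better chance of showing both effects

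*Combined protocol and SAP*

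**What the plan says.** Section 6.2 opens with "The primary aim involves two pair-wise comparisons of equal importance". It then sets the level: "For each comparison, we fix the probability of a Type I error at 0.025", and gives the reason: "in order to maintain the overall probability of a Type I error at 0.05". Section 6.0 names the comparisons, each tested by a Cochran-Mantel-Haenszel (CMH) test over the randomization strata: "1) PA and C, and (2) PA+PCP and C in an intent-to-treat analysis". Section 6.0 also plans stratum-adjusted differences in proportions but states no confidence level for them.

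The hypothesis in section 2.2 covers both interventions: "women randomized to PA and PA+PCP will have significantly higher rates of breast cancer surveillance" than controls. PA+PCP versus PA is a secondary objective (2.1.1) and lies outside this pair.

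Table 1 gives power for one comparison at a time: 83%, 90% and 80%. No section gives the power to show both effects. No section mentions a step-down rule or any passing of alpha from one comparison to the other.

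**The concern.** The only reason given for the fixed split is to keep the overall Type I error at 0.05. Holm's rule meets that aim whatever the dependence between the tests, including the dependence created by a shared control arm. It treats the two comparisons alike, as equal importance requires, and it can never reject less than the fixed split.

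The difference appears when one comparison is clearly significant and the other has a p-value between 0.025 and 0.05. The plan would then leave the second effect unproven, although the overall error rate allows it to be claimed. Because section 2.2 predicts that both interventions beat control, that outcome matters to this trial.

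**Working it through.** **Inputs.** Two comparisons, two-sided tests, 0.025 each, 1:1:1 allocation, control rates of 10% or 15% (section 6.2 and Table 1). The documents imply two arm sizes. Section 3.0 says "Participants will be recruited in three waves (97/wave"), so 3 × 97 = 291, or 97 per arm. It also says "We will enroll 320 women from the Childhood Cancer Survivor Study (CCSS"), so 320/3 ≈ 107 per arm. Both are carried through.

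**1. The split is valid.** 0.025 + 0.025 = 0.05. The attained overall error would be 1 − 0.975² = 0.0494 if the tests were independent. It is about 0.0465 at a correlation of 0.5, which equal arms sharing a control produce.

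**2. Reproducing Table 1.** Normal approximation with pooled variance under the null, where p̄ is the mean of the two rates and z = 2.2414 for two-sided 0.025:

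power = Φ{[(p₂ − p₁)√n − z√(2p̄(1 − p̄))] / √[p₁(1 − p₁) + p₂(1 − p₂)]}

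For 10% vs 30% and n = 97: (1.970 − 2.2414 × 0.5657)/0.5477 = 1.281, so power is 90.0% (Table 1: 90%). For 10% vs 28% it is 83.6% (Table 1: 83%). For 15% vs 35% it is 84.2%, against 80% in Table 1. With 107 per arm and a continuity correction the three values are 83.3%, 90.1% and 84.3%. So two settings reproduce the first two rows, and neither reproduces the third. The documents do not say which sample size underlies the table.

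**3. Why Holm holds 0.05.** If neither intervention works, a false rejection needs the smaller p-value to be at most 0.025, which has probability at most 0.05. If only one works, a false rejection needs the other's p-value to be at most 0.05, again with probability at most 0.05. If both work, no rejection is false.

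**4. Power under the two rules.** Simulation of 200,000 trials per scenario: shared control, two-sided CMH without continuity correction over the 8 strata (2 × 2 × 2 from section 3.2), and strata balanced across arms. The assumed stratum shares are 22, 18, 15, 12, 11, 9, 8 and 5%. Rates are common across strata, as section 6.2 assumes. Each cell reads fixed split → Holm.

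| Control / both interventions | n per arm | Each comparison | Both significant | At least one |
|---|---|---|---|---|
| 10% / 30% | 97 | 91.0% → 94.0% | 84.7% → 90.6% | 97.4%, same |
| 10% / 30% | 107 | 93.6% → 95.9% | 88.8% → 93.5% | 98.4%, same |
| 15% / 35% | 97 | 84.8% → 88.9% | 75.4% → 83.5% | 94.3%, same |
| 15% / 35% | 107 | 88.3% → 91.8% | 80.5% → 87.5% | 96.2%, same |

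For 10% / 28%, both significant goes from 75.2% to 83.4% at 97 per arm and from 80.5% to 87.5% at 107.

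**5. Internal check.** With equal effects, P(both) + P(at least one) = 2 × P(each). For 10% / 30% at 97 per arm, the fixed split gives 2 × 91.0 − 97.4 = 84.6 and Holm gives 2 × 94.0 − 97.4 = 90.6, matching the table to rounding. Since the chance of at least one cannot change, the gain in showing both is twice the gain per comparison.

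**6. Cross-check.** Exact binomial enumeration with an unstratified pooled z-test gives, for both significant, 84.8% → 90.7% (97) and 89.1% → 93.5% (107) for 10% / 30%. For 15% / 35% it gives 75.9% → 83.8% and 80.7% → 87.7%.

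**7. What Holm gives up.** If neither works (10% in all arms), any rejection has probability 0.0445 at 97 and 0.0456 at 107, identical under both rules. If only PA+PCP works (control 10%, PA 10%, PA+PCP 30%), the false-positive rate for PA rises from 0.025 to 0.047 at 97 and from 0.024 to 0.046 at 107. That rate is then the overall error, and it stays below 0.05.

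**8. Unequal effects.** Section 2.0 expects provider activation to raise rates beyond patient activation alone. As an illustration, with PA at an assumed 20%, PA+PCP at 30% and control at 10%, both significant goes from about 38% to 49% at 97 per arm and from 42% to 53% at 107.

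**The case against.** The plan contains no defect. It states a valid rule and a reason for it. The rule is simple, and it pairs directly with 97.5% intervals for the two differences. The trial is powered per comparison and the documents set no target for showing both effects. On the plan's own measure the gain at 97 per arm is 3.0 points (94.0 − 91.0) or 4.1 points (88.9 − 84.8). All of this stands, and it keeps the point at the level of an optional improvement. It does not show any power advantage for the fixed split, because there is none.

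The more serious objection is timing. Section 4.0 describes a final attempt to collect outcomes "from 63 participants who are more than 3 months past the approximated 18-month study window", so follow-up is well advanced. Appendix IV lists outcomes among the contents of the monitoring board's reports, has the principal investigators prepare its routine reports, and lets the board request analyses from them. It does not say whether outcomes are shown by arm. A late move to a rule that can only add rejections will be challenged unless it is shown to have been blind to comparative results. This stands as a condition on the remedy.

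Two smaller points also stand. Every rejection Holm adds has a p-value between 0.025 and 0.05, so a 97.5% interval that agrees with the test will include zero. And the 15% vs 35% scenario, where the gain in the main table is largest, is the Table 1 row that does not reproduce. The direction does not depend on that. With a continuity correction at 97 per arm the formula gives 79.7%, close to the stated 80%, and in an unstratified simulation with that correction both significant still rises, from 68.9% to 78.1%.

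**Conclusion.** The concern holds as a low-priority point of efficiency. The fixed split controls the overall error as intended, and keeping it would not be wrong. Holm controls the same error and raises the chance of confirming both parts of the section 2.2 hypothesis by about 5 to 8 points in the Table 1 scenarios. The chance of at least one significant result, and the sample size, are unaffected.

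That Holm rejects at least as much and keeps the error at or below 0.05 does not depend on any assumption about effects. The size of the gain does. The tabulated figures assume equal true rates in the two intervention arms, a common rate across strata, the stratum shares listed above, and 97 or 107 women per arm.

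**What to change.** If those making the change have not seen outcomes by arm, add to sections 6.0 and 6.2:

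- The two primary CMH p-values are ordered. The smaller is tested at two-sided 0.025. If it is significant, the larger is tested at two-sided 0.05; otherwise neither effect is claimed.
- Significance is judged by this step-down rule. Confidence intervals for the stratum-adjusted differences are descriptive, and their level is stated.
- The power computed at 0.025 is kept as a lower bound for each comparison.

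Date the change, and record who had access to outcomes by arm at that time, including through reports to the monitoring board. If blindness to comparative results cannot be documented, leave the fixed split in place.

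The cost is a few sentences of SAP text and that record, with no added participants or data. The plan should state two downsides: the higher false-positive rate for the second comparison when only one intervention works (about 0.025 to just under 0.05, within the overall 0.05), and the loss of simple 97.5% intervals that match the test decisions.
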